## 4 Endpoints and Assessment Methods

### 4.1 Primary Endpoints and Assessment Methods

See Section 9.1 of the protocol.

### 4.2 Secondary Endpoints and Assessment Methods

See Section 9.2 of the protocol.

### 4.3 Observational Endpoints and Assessment Methods

There are no observational objectives in this study.

### 4.4 Derived Endpoints: Calculation Methods

#### 4.4.1 Safety

The solicited period for solicited injection site reactions is from Day (D) 0 to D7 and from D0 to D14 for solicited systemic reactions.

Table 4.1, Table 4.2, and Table 4.3 present, respectively, the injection site reactions and systemic reactions that are prelisted in the DCs and case report form (CRF) for the different age group, together with the intensity scales.

**Table 4.1: Solicited injection site reactions: terminology, definitions, and intensity scales for subjects aged 9 to 11 years**

| CRF term
(MedDRA
lowest level
term [LLT]) | Injection site pain   | Injection site erythema   | Injection site swelling  |
|--|---|---|--|
| DC term  | Pain  | Redness   | Swelling   |
| Definition   |   | Presence of a redness including the approximate point of needle entry           | Swelling at or near the injection site
Swelling or edema is caused by a fluid infiltration in tissue or cavity and, depending on the space available for the fluid to disperse, swelling may be either soft (typically) or firm (less typical) to touch and thus can be best described by looking at the size of the swelling |
| Intensity scale*                                   | Grade 1: Easily tolerated

Grade 2: Sufficiently discomforting to interfere with normal behavior or activities

Grade 3: Incapacitating, unable to perform usual activities | Grade 1: > 0 to < 25 mm

Grade 2: ≥ 25 to < 50 mm

Grade 3: ≥ 50 mm | Grade 1: > 0 to < 25 mm

Grade 2: ≥ 25 to < 50 mm

Grade 3: ≥ 50 mm  |

\* For the subjective reaction of pain, subjects or parents/legally acceptable representatives recorded the intensity level (Grade 1, 2, or 3) in the DC. For the measurable reactions of redness and swelling, they recorded the size of the reaction and the classification as Grade 1, 2, or 3 will be assigned at the time of the statistical analysis.

**Table 4.2: Solicited injection site reactions: terminology, definitions, and intensity scales for subjects aged >= 12 years**

| CRF term
(MedDRA
LLT) | Injection site pain   | Injection site erythema  | Injection site swelling  |
|-----------------------------|---|--|--|
| DC term                     | Pain  | Redness  | Swelling   |
| Definition                  |   | Presence of a redness including the approximate point of needle entry                            | Swelling at or near the injection site
Swelling or edema is caused by a fluid infiltration in tissue or cavity and, depending on the space available for the fluid to disperse, swelling may be either soft (typically) or firm (less typical) to touch and thus can be best described by looking at the size of the swelling |
| Intensity scale*            | Grade 1: No interference with activity
Grade 2: Some interference with activity
Grade 3: Significant; prevents daily activity | Grade 1: $\geq 25$ to $\leq 50$ mm
Grade 2: $\geq 51$ to $\leq 100$ mm
Grade 3: $> 100$ mm | Grade 1: $\geq 25$ to $\leq 50$ mm
Grade 2: $\geq 51$ to $\leq 100$ mm
Grade 3: $> 100$ mm   |

\* For the subjective reaction of pain, subjects/parents/legally acceptable representatives recorded the intensity level (Grade 1, 2, or 3) in the DC. For the measurable reactions of redness and swelling, they recorded the size of the reaction and the classification as Grade 1, 2, or 3 will be at the time of the statistical analysis

**Table 4.3: Solicited systemic reactions: terminology, definitions, and intensity scales for all subjects**

| CRF term
(MedDRA
LLT) | Fever  | Headache  | Malaise  | Myalgia  | Asthenia  |
|-----------------------------|--|---|--|--|---|
| DC term                     | Temperature  | Headache  | Feeling unwell   | Muscle aches and pains   | Weakness  |
| Definition           | Elevation of temperature to $\geq 38.0^{\circ}\text{C}$ ( $\geq 100.4^{\circ}\text{F}$ )   | Pain or discomfort in the head or scalp. Does not include migraine.   | General ill feeling. Malaise is a generalized feeling of discomfort, illness, or lack of well-being that can be associated with a disease state. It can be accompanied by a sensation of exhaustion or inadequate energy to accomplish usual activities. | Muscle aches and pains are common and can involve more than one muscle at the same time. Muscle pain can also involve the soft tissues that surround muscles. These structures, which are often referred to as connective tissues, include ligaments, tendons, and fascia (thick bands of tendons). Does not apply to muscle pain at the injection site which should be reported as injection site pain. | Generalized weakness.   |
| Intensity scale*     | Grade 1: $\geq 38.0^{\circ}\text{C}$ to $\leq 38.4^{\circ}\text{C}$ ,
or $\geq 100.4^{\circ}\text{F}$ to $\leq 101.1^{\circ}\text{F}$

Grade 2: $\geq 38.5^{\circ}\text{C}$ to $\leq 38.9^{\circ}\text{C}$ ,
or $\geq 101.2^{\circ}\text{F}$ to $\leq 102.0^{\circ}\text{F}$

Grade 3: $\geq 39.0^{\circ}\text{C}$
or $\geq 102.1^{\circ}\text{F}$ | Grade 1: No interference with activity

Grade 2: Some interference with activity

Grade 3: Significant; prevents daily activity | Grade 1: No interference with activity

Grade 2: Some interference with activity

Grade 3: Significant; prevents daily activity  | Grade 1: No interference with activity

Grade 2: Some interference with activity

Grade 3: Significant; prevents daily activity  | Grade 1: No interference with activity

Grade 2: Some interference with activity

Grade 3: Significant; prevents daily activity |

\* For all reactions but fever, subjects or parents/legally acceptable representatives recorded the intensity level (Grade 1, 2, or 3) in the DC. For fever, they recorded the body temperature and the classification as Grade 1, 2, or 3 will be assigned at the time of the statistical analysis.

#### 4.4.1.1 **Solicited Reactions**

##### 4.4.1.1.1 **Daily Intensity**

Intensity will be categorized as follows: None, Grade 1, Grade 2, Grade 3, or Missing. The daily intensity will be recorded by the Investigator for solicited reactions whose scale is not a measure. For measurable solicited reactions, the intensity will be calculated at the time of the statistical analysis based upon the intensity scales defined in the protocol.

A reaction that is too large to measure (non-measurable [NM]) will be considered as Grade 3.

##### 4.4.1.1.2 **Maximum Overall Intensity**

Maximum overall intensity is derived from the daily intensities and is calculated as the maximum of the daily intensities over the period considered. The maximum intensity during the solicited period will be computed without considering the ongoing period.

Note: The maximum overall intensity should be considered as "Missing" only if all daily intensities over the period considered are "Missing."

##### 4.4.1.1.3 **Presence**

Presence of solicited reactions will be computed based on daily records during the solicited period. For any specific period, a subject would be considered to have a reaction if the intensity is greater than or equal to Grade 1 for at least one day during that period. If no data is recorded and the presence recorded by the Investigator is different from "No", the presence will be considered as "Missing."

##### 4.4.1.1.4 **Time of Onset**

Time of onset is derived from the daily intensities. It corresponds to the first day with intensity of Grade 1, Grade 2, or Grade 3.

Note: If a reaction is not continuous (i.e., reaction occurs over two separate periods of time intervened by at least one daily intensity "Missing" or "None") then the time of onset is the first day of the first occurrence.

Time of onset will be displayed by period as follows:

**Table 4.4: Categories for Time of Onset**

| Period of Time of Onset                     |  |
|---|--|
| Injection Site Reactions
(D0-D7) | Systemic Reactions
(D0-D14) |

| Period of Time of Onset |          |
|-------------------------|----------|
| D0 - D3                 | D0 - D3  |
| D4 - D7                 | D4 - D7  |
|                         | D8 - D14 |

#### 4.4.1.1.5 Number of Days of Occurrence

The “number of days of occurrence” of a solicited reaction during the solicited period is computed as the number of days the solicited reaction is present, (intensity different from none or missing between D0 and the end of the solicited period), over the daily record period. For instance, for calculating number of days of fever occurrence, only daily temperature  $\geq 38^{\circ}\text{C}$  will be considered.

Number of days of occurrence during and after the solicited period will be displayed by category (range) as follows:

**Table 4.5: Categories for Number of Days of Occurrence**

|                         | Period of Number of Days of Occurrence |  |
|-------------------------|--|--|
|                         | Injection Site Reactions               | Systemic Reactions                           |
| During solicited period | 1-3 days
4-7 days
8 days         | 1-3 days
4-7 days
8-14 days
15 days |

#### 4.4.1.1.6 Overall Number of Days of Occurrence

If a reaction is ongoing at the end of the solicited period, then the overall number of days of occurrence is derived from the daily intensities and the stop date of the reaction after the end of the solicited period. The overall number of days of occurrence is:

- $(\text{stop date} - \text{last vaccination date}) + (\text{number of days of occurrence within the solicited period}) - \text{length of the solicited period} + 1$

If the stop date is missing or incomplete (contains missing data [MD]), the overall number of days of occurrence will be considered as "Missing".

**Table 4.6: Categories for Overall Number of Days of Occurrence**

|   | Period of Overall Number of Days of Occurrence |   |
|---|--|---|
|   | Injection Site Reactions                       | Systemic Reactions  |
| Ongoing period after D7 for injection site/D14 for systemic reactions | 1-3 days
4-7 days
≥ 8 days
Missing    | 1-3 days
4-7 days
8-14 days
≥ 15 days
Missing |

#### 4.4.1.1.7 Ongoing

Ongoing is derived from the last daily intensity of the solicited period and the maximum intensity of the ongoing period.

If the last daily intensity of the solicited period is Grade 1, Grade 2, or Grade 3 and maximum intensity of the ongoing period is also Grade 1, Grade 2, or Grade 3, then the reaction is considered ongoing. In any other case, the reaction will not be considered as ongoing.

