## **5.3 Handling of Missing Data and Outliers**

### **5.3.1 Safety**

No replacement will be done.

In all subject listings, partial and missing data will be clearly indicated as missing.

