#### **5.3.1.4 Intensity**

For solicited reactions, missing intensities will be handled as described in Section 4.4.1.1.1.

For unsolicited non-serious AEs, missing intensities will remain missing and will not be imputed.

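### SAP 4.4.1.1.7 treats a blank intensity like a recorded None and ignores the stop date, so some persisting solicited reactions drop out of Table 4.6

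*SAP*

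**What the plan says.** SAP 4.4.1.1.7 names the two inputs to the flag: "Ongoing is derived from the last daily intensity of the solicited period and the maximum intensity of the ongoing period". Both must be Grade 1, 2 or 3. The default for all other combinations is "In any other case, the reaction will not be considered as ongoing".

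Missing is a value in its own right. SAP 4.4.1.1.1 states: "Intensity will be categorized as follows: None, Grade 1, Grade 2, Grade 3, or Missing". On blanks, SAP 5.3.1.4 only points back: "For solicited reactions, missing intensities will be handled as described in Section 4.4.1.1.1". That section lists the category and adds no rule for it. SAP 5.3.1 says of safety data in general: "No replacement will be done".

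The stop date enters only after the flag has been set. SAP 4.4.1.1.6 opens: "If a reaction is ongoing at the end of the solicited period, then the overall number of days of occurrence is derived from" the daily grades and the stop date. Within that branch, a missing or partial stop date gives an overall day count of Missing. Table 4.6 displays the overall count for the period after D7 or D14 and has a Missing row.

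**The concern.** A blank is not evidence that a reaction was absent, yet the flag gives it the same consequence as a recorded None. The stop date is the item that most directly shows whether a reaction outlasted the solicited period, and the flag does not look at it. A record can therefore carry a stop date several days after D7 or D14 and still be kept out of the table meant for such reactions.

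The rule also differs from its neighbours, which keep an unknown visible or treat it cautiously. Maximum intensity (4.4.1.1.2) and presence (4.4.1.1.3) each have a Missing outcome. Missing causality is taken as related (5.3.1.2). Unsolicited events with unknown onset stay in the tables (5.3.1.5).

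At stake is the description of how long reactions persist under concomitant and sequential vaccination. Protocol 9.2.2.2 lists duration and number of days among the safety descriptors. Protocol 9.2.2.3.2 has the diary completed until the reaction resolves, so the later data are meant to be collected.

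**Working it through.** The plan states no figure on this point, so there is none to reproduce. The check applies the SAP rules to example records. The diary patterns and stop days are assumed for illustration.

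**Inputs**
- Period length (SAP 4.4.1): D0 to D7 is 7 − 0 + 1 = 8 days; D0 to D14 is 14 − 0 + 1 = 15 days.
- In-period days (4.4.1.1.5): diary days that are neither None nor Missing.
- Overall days (4.4.1.1.6): days from vaccination to stop, plus in-period days, minus period length, plus 1.
- Flag (4.4.1.1.7): ongoing only if the final diary day and the highest later grade are both Grade 1 to 3.

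**Check of the formula on complete records.** Injection site reaction graded every day, stop D12: 12 + 8 − 8 + 1 = 13, which is D0 to D12. Systemic reaction graded every day, stop D20: 20 + 15 − 15 + 1 = 21, which is D0 to D20. The formula is sound with lengths 8 and 15.

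**Effect of one blank**

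| Graded days, stop day | Blank item | In-period days | Flag | Overall days if the stop date were used | Table 4.6 under the SAP |
|---|---|---|---|---|---|
| Injection site D0–D7, D12 | none | 8 | ongoing | 13 | counted, 8 days or more |
| Injection site D0–D6, D12 | D7 | 7 | not ongoing | 12 + 7 − 8 + 1 = 12 | absent |
| Injection site D0–D7, D12 | later grade | 8 | not ongoing | 12 + 8 − 8 + 1 = 13 | absent |
| Injection site D6–D7, D12 | later grade | 2 | not ongoing | 12 + 2 − 8 + 1 = 7 | absent |
| Systemic D0–D14, D20 | none | 15 | ongoing | 21 | counted, 15 days or more |
| Systemic D0–D13, D20 | D14 | 14 | not ongoing | 20 + 14 − 15 + 1 = 20 | absent |
| Systemic D0–D14, D20 | later grade | 15 | not ongoing | 20 + 15 − 15 + 1 = 21 | absent |

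In every row with a blank, the recorded stop date places the end of the reaction 5 days (12 − 7) or 6 days (20 − 14) after the solicited period, and the reaction is still absent from Table 4.6. A record with None on the final day gets the same flag as one with that day blank.

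The in-period column feeds Table 4.5. It does not depend on the flag, so it is the same under the SAP rule and under the fix below.

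**The case against.** The strongest defence is that the SAP has a consistent convention: a day without data is not counted as a day with the reaction. Section 4.4.1.1.4 lets a Missing day interrupt a reaction just as None does, 4.4.1.1.5 counts only graded days, and 5.3.1 rules out replacement. On that view 4.4.1.1.7 merely follows suit. This stands as a reason not to fill in blank diary days. It does not explain passing over a stop date that was recorded, since using it replaces nothing.

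Blanks should also be uncommon. Sites interview families and try to resolve incomplete diaries (Protocol 11.1), and missing or discrepant diary entries are clarified verbally and transferred to the CRF (Protocol 13.2). A late stop date beside a blank grade is the kind of record these steps should catch. The CRF is not among the documents, so it cannot be seen whether that combination can survive data entry. This limits the size of the problem but leaves the rule as it is.

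It could also be argued that the final intensity means the last one recorded. The SAP does not say so. Even then, only records with a blank final day would be resolved; those with a blank later grade would not.

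Finally, all safety analyses are descriptive (SAP 5.1.2.2), the same rule applies to both groups, and presence, onset and in-period maximum intensity do not use the flag. All of this stands, and it makes the point minor.

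**Conclusion.** The point holds as a minor defect in a derivation rule. Read literally, 4.4.1.1.7 drops from Table 4.6 a reaction that has one blank intensity and a recorded stop date after D7 or D14, so persisting reactions are under-counted there. The size is unknown: the documents give no frequency of blanks, and any percentage would rest entirely on assumed rates. The conclusion assumes that the CRF can hold a stop date beside a blank intensity.

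Three stronger readings are tempting, and the documents do not support them.
- A reader might infer that prolonged reactions are moved into short-duration categories. Table 4.5 counts in-period days for every reaction under either rule, and no section assigns an overall day count to a reaction that is not ongoing. The reaction is absent from Table 4.6; it is not relabelled as short.
- A reader might infer that 4.4.1.1.7 contradicts the Missing outcome of 4.4.1.1.6. That outcome belongs to the branch for ongoing reactions and still serves those without a usable stop date.
- A reader might infer a bias between the groups. Nothing in the documents suggests that blanks differ by group.

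**What to change.** Amend SAP 4.4.1.1.7 for the case where exactly one of the two intensities is blank and the other is Grade 1 to 3:
- recorded stop date after D7 (injection site) or D14 (systemic): ongoing;
- recorded stop date within the solicited period: not ongoing;
- stop date missing or partial: set the flag to Missing and count the reaction in the Missing row of Table 4.6.

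Keep not ongoing for a recorded None on the final day. Do not carry earlier diary days forward across several blank days: that would let one graded day at D0 stand for an otherwise empty diary. Report the number of reactions affected, by group.

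The cost is one paragraph of SAP text and one programming rule, using items the SAP's derivations already rely on. No endpoint, hypothesis or clinical procedure changes. The downside is that a few more reactions appear as prolonged or Missing.

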#### 4.4.1.2 Unsolicited Non-serious AEs

##### 4.4.1.2.1 Intensity

Intensity will be categorized as follows: None, Grade 1, Grade 2, Grade 3, or Missing. For unsolicited non-serious adverse events (AEs) the intensity will be recorded by the Investigator for AEs whose scale is not a measure. For measurable AEs that have the same preferred term (PT) as a solicited reaction, the intensity will be calculated at the time of the statistical analysis.

##### 4.4.1.2.2 Last Vaccination

Last vaccination before an unsolicited non-serious AE is derived from the visit numbers provided in the clinical database and is calculated as follows:

- If an unsolicited non-serious AE has a non-missing visit number, the visit number should be used to determine the last vaccination before the unsolicited non-serious AE
- If the visit number is missing, then the start date should be used to determine the last vaccination before the unsolicited non-serious AE

##### 4.4.1.2.3 Time of Onset

Time of onset in days following the vaccination will be computed as follows:

- Time of onset = start date – date of previous vaccination

If the start date of the AE is the same as the last vaccination date, then the onset is “0”.

If one of the dates is partially missing, time of onset will be considered as “Missing”. Events that occur before vaccination (negative time of onset) will not be included in the analyses but will be listed separately. The unsolicited non-serious AEs will be analyzed within 28 days after vaccination, which corresponds to AEs with a time of onset between 0 and 28 days after vaccination or missing. An AE with missing time of onset will be considered to have occurred just after the vaccination indicated by the visit number, so will be included in these tables.

Time of onset will be displayed by period as follows:

- D0-D3
- D4-D7
- D8-D14
- $\geq$  D15
- Missing

#### 4.4.1.2.4 Duration

The duration will be computed as: Duration = stop date of event - start date of event + 1.

If start or stop dates are unfilled (“blank”) or missing (contain “MD”) or ongoing is ticked, then the duration will be considered as “Missing.”

If the start date of the AE is the same as the last vaccination date, then the duration is 1 day.

Duration will be displayed by period as following:

- 1-3 days
- 4-7 days
- 8-14 days
- 15 days or more
- Missing

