9.2.2.2 Safety Endpoints

Safety endpoints for Gardasil and CYD dengue vaccine safety in each group are:

- Occurrence of immediate AEs reported within 30 minutes after each and any injection
- Occurrence of solicited (i.e., pre-listed in the subject's diary card [DC] and electronic case report form [CRF]) injection site reactions (pain, erythema, and swelling) occurring up to 7 days after each and any injection
- Occurrence of solicited systemic reactions (fever, headache, malaise, myalgia, and asthenia) occurring up to 14 days after each and any injection
- Occurrence of unsolicited AEs occurring up to 28 days after each and any injection
- Occurrence of non-serious AESIs* occurring within 7 days following each and any injection
- Occurrence of SAEs, including serious AESIs* (with specific time windows according to the type of AESI*) throughout the trial
- Occurrence of hospitalized VCD cases throughout the trial (i.e., from D0 through end of the study)
- * Hypersensitivity/allergic reactions (serious or not) within 7 days after each CYD dengue vaccine injection, serious viscerotropic disease within 30 days after each CYD dengue vaccine injection, serious neurotropic disease within 30 days after each CYD dengue vaccine injection; serious dengue cases requiring hospitalization (i.e., hospitalized suspected dengue case) occurring in all subjects at any time during the study.

Depending on the item, these could include: nature (Medical Dictionary for Regulatory Activities [MedDRA] preferred term), time of onset, duration, number of days of occurrence, grade of severity, relationship to vaccine, action taken, whether the event/reaction led to early termination from the study, seriousness, or outcome.

Hospitalized suspected dengue case is defined as an acute febrile illness with diagnosis of dengue requiring hospitalization (with bed attribution). In such cases, 1 unplanned acute blood sample (within the first 5 days after fever onset) will be collected for virological confirmation of hospitalized suspected dengue case. A suspected case will be considered VCD if there is a detection of WT dengue virus by dengue NS1 Ag ELISA and/or dengue RT-PCRs (at the GCI or GCI designated laboratory).

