#### **4.4.1.3.3 Duration**

Duration will be computed using the same methodology as for unsolicited non-serious AEs described in Section 4.4.1.2.4 .

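### The SAP's duration rule gives unsolicited AEs and SAEs that start on a vaccination day a duration of 1 day, contradicting its own formula for any such event that ends later

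*SAP*

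**What the plan says.** SAP 4.4.1.2.4 covers unsolicited non-serious AEs and contains three rules.

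- The general definition: "Duration = stop date of event - start date of event + 1".
- A rule for incomplete records. If a start or stop date is blank or missing, "or ongoing is ticked, then the duration will be considered as “Missing".
- A rule for day-0 events: "If the start date of the AE is the same as the last vaccination date, then the duration is 1 day".

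The section then lists the display bands: 1–3 days, 4–7 days, 8–14 days, 15 days or more, and Missing.

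For SAEs, SAP 4.4.1.3.3 says: "Duration will be computed using the same methodology as for unsolicited non-serious AEs described in Section 4.4.1.2.4". All three rules therefore apply to SAEs as well.

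Under SAP 4.4.1.2.2, the last vaccination is the one preceding the event. The day-0 rule therefore operates after every dose, not only the final one. SAP 4.4.1.2.3 uses the same opening clause for onset: "If the start date of the AE is the same as the last vaccination date, then the onset is" 0.

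Protocol 9.2.2.2 includes duration among the attributes that may be described for the safety endpoints: "time of onset, duration, number of days of occurrence, grade of severity".

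**The concern.** Comparing the start date with the vaccination date tells us when an event began, not how long it lasted. In the onset section the comparison gives the right answer, because start date minus vaccination date is 0. In the duration section the answer of 1 day agrees with the formula only if the event also stops on that day, and the formula already returns 1 in that case. The extra sentence is therefore either redundant or wrong.

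What is at stake is the duration output for unsolicited AEs and SAEs that begin on an injection day. Day-0 onset lies inside the 28-day window analysed under SAP 4.4.1.2.3. It includes every immediate unsolicited systemic AE (within 30 minutes, Protocol 9.2.2.3.1), since such an event must start on the vaccination day. Any error goes in one direction, towards shorter events, and a literal program would give no visible sign of it.

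**Working it through.** The plan states no figure to reproduce here. The check applies its two rules to the same hypothetical records.

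**Inputs**

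- Formula (SAP 4.4.1.2.4): duration = stop − start + 1.
- Day-0 rule (SAP 4.4.1.2.4): duration = 1 if start = last vaccination date.
- Bands (SAP 4.4.1.2.4): 1–3, 4–7, 8–14, 15 or more days.
- Days are counted from the preceding vaccination (D0).

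**Events starting on D0 with a complete stop date**

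| Stop | Formula | Band by formula | Day-0 rule | Band by day-0 rule |
|---|---|---|---|---|
| D0 | 0 − 0 + 1 = 1 | 1–3 | 1 | 1–3 |
| D1 | 1 − 0 + 1 = 2 | 1–3 | 1 | 1–3 |
| D2 | 2 − 0 + 1 = 3 | 1–3 | 1 | 1–3 |
| D3 | 3 − 0 + 1 = 4 | 4–7 | 1 | 1–3 |
| D7 | 7 − 0 + 1 = 8 | 8–14 | 1 | 1–3 |
| D12 | 12 − 0 + 1 = 13 | 8–14 | 1 | 1–3 |
| D14 | 14 − 0 + 1 = 15 | 15 or more | 1 | 1–3 |
| D28 | 28 − 0 + 1 = 29 | 15 or more | 1 | 1–3 |

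The value is wrong against the SAP's own formula from a stop date of D1 onwards, by the true duration minus 1 day. The band is wrong from a stop date of D3 onwards, that is, for true durations of 4 days or more.

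**Comparison with events starting on D1**

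The day-0 rule does not apply to these. D1 to D14 gives 14 − 1 + 1 = 14 days. An event that starts one day earlier and stops on the same day, D0 to D14, is recorded as 1 day instead of 15. Nothing in either document explains that discontinuity.

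**Day-0 events without a usable stop date**

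The incomplete-record rule returns Missing and the day-0 rule returns 1 day. The section does not say which prevails, so the result is undetermined.

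**Is the sentence limited elsewhere?**

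No other section of the SAP or protocol restricts it to events that also end on the vaccination day.

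**The case against.** The strongest reply is that this is a drafting slip with little consequence. The correct formula comes first, and the opening clause of the disputed sentence matches the onset section word for word, so a programmer may well ignore it. The output is descriptive: SAP 5.1.2.2 tests no safety hypotheses, and for unsolicited events Table 5.1 calls for counts and percentages of subjects and numbers of events, which do not use duration. The protocol's list of attributes is also permissive, saying what descriptions could include depending on the item.

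Much of this stands, and it limits the consequence. It does not remove the contradiction. That the sentence is a slip is plausible but is an inference; the SAP does not say so, and the section does specify a banded duration display.

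Four stronger readings are tempting, and the documents do not support them.

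- *A reader might infer that all day-0 reactions are affected.* Solicited reactions have their own derivations, days of occurrence (4.4.1.1.5) and overall days of occurrence (4.4.1.1.6), which the sentence does not touch.
- *A reader might infer that every day-0 unsolicited event is misreported.* A 1-day event is correct, and events of 2 or 3 days stay in the right band even though their value is wrong.
- *A reader might infer that an unresolved day-0 SAE will be shown as lasting 1 day.* The Missing rule applies to the same record, so the outcome is unspecified, not established.
- *A reader might infer that the vaccines' safety profile will look materially more transient.* Neither document gives counts or durations of day-0 unsolicited events, so the size of any distortion is unknown. A full schedule has three vaccination days in Group 1 and five in Group 2 (Protocol 5.1.3), but those are opportunities for the rule to operate, not affected events.

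**Conclusion.** The rule is wrong as written. For unsolicited non-serious AEs and SAEs that start on the day of the preceding vaccination and have a complete, later stop date, the day-0 sentence contradicts the SAP's formula and understates duration by the true duration minus 1 day. Events truly lasting 4 days or more are misplaced in the 1–3 day band. For day-0 events with a missing stop date or ongoing ticked, there is an unresolved conflict between Missing and 1 day.

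The effect is confined to derived duration and the tables that use it. Recorded start and stop dates, incidence, solicited reactions and all non-inferiority tests are unchanged. The conclusion on understated durations assumes that the sentence is programmed literally; the documents do not show whether it was. The number of affected events cannot be calculated from them.

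This should be corrected because it is a definite error in a stated derivation, but it does not bear on the trial's primary conclusions.

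**What to change.** In SAP 4.4.1.2.4, delete the day-0 sentence, or replace its reference to the last vaccination date with the stop date, so that it reads: *if the start date of the AE is the same as the stop date, the duration is 1 day*. State that stop − start + 1 applies to all events with complete dates, including those with onset on the vaccination day, and that duration is Missing whenever a date is missing or ongoing is ticked. Section 4.4.1.3.3 then inherits the correction for SAEs without further change.

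The cost is one sentence in the SAP and one line of derivation code. If the derivation has already been programmed, check which rule was coded. No information is lost, because the formula already returns 1 day for events that start and stop on the same day.
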